### 15.3 Primary Analysis – 72-Hour Survival

The primary hypothesis is that there is no difference in OHCA 72-hour survival between primary LT- and primary-ETI airway management strategies. The primary outcome of interest is 72-hour survival. We will calculate the difference in outcomes divided by the estimated “robust” standard error based on the Huber-White sandwich estimator in order to account for within cluster correlation and variability, which might depart from the classical assumptions. To quantify the treatment effect, we will calculate the 95% CI for the difference in event rates. Since

[figure not shown]

Figure 12 - Anticipated CONSORT Diagram

randomization includes all eligible OHCA patients, we will not stratify the primary analysis by initial cardiac rhythm. We will perform the analysis on intention-to-treat (primary) as well as as-treated (secondary) bases.

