## **15.5 Subgroup Analyses**

OHCA outcomes are known to vary for different patient subsets. For example, OHCA survival is approximately 28.4% for patients with an initial “shockable” cardiac rhythms (ventricular fibrillation or tachycardia) and 6.2% for non-shockable rhythms (pulseless electrical activity and asystole). We will explore multiplicative associations between airway management strategy (ETI vs. LT) and the pertinent subgroups, including:

- Initial cardiac rhythm (shockable vs. non-shockable);
- Bystander witnessed arrest (yes vs. no);
- EMS response time (911 call to arrival on-scene: <10 vs. ≥10 mins);
- BLS unit capability of performing LT insertion (yes vs. no);
- Time of airway placement after rescuer arrival on-scene (early [<10 minutes] vs. later [≥10 minutes]);
- Use of NMB (RSI) before or during airway insertion efforts (yes vs no);
- Age (<65 vs. ≥65 years).
- Placement of advanced airway after ROSC.
- Initial airway management with non-rebreather mask only (passive ventilation).

Initial airway management with video laryngoscopy. If an [airway x subgroup] interaction is statistically significant, we will stratify the analysis by the subgroup.

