## 16.2 Interim Monitoring Plan and Stopping Boundaries – Criteria for Terminating the Trial

With input from the Data Safety and Monitoring Board (DSMB), prior to initiation of the trial, we will develop a monitoring plan to guide early termination of the trial. Factors influencing stopping decision may include (a) formal stopping rules based upon the primary analysis, (b) information on safety outcomes by treatment group, (c) consistency between results for primary and secondary outcomes, and (d) consistency of treatment effects across subgroups.

			Lower Stopping Boundary (SGA Better)			
Analysis	Cum. Sample Size	Prop. Max Stat Info	Absolute Difference	Adjusted Difference	95% Confidence Interval	P-value
1	654	0.25	-0.108	-0.098	(-0.154, -0.041)	0.001
2	1,306	0.50	-0.102	-0.092	(-0.135, -0.053)	<0.001
3	1,958	0.75	-0.092	-0.084	(-0.120, -0.052)	<0.001
4	2,612	1.00	-0.029	-0.029	(-0.059, 0.000)	0.050

			Upper Stopping Boundary (ETI Better)			
Analysis	Cum. Sample Size	Prop. Max Stat Info	Absolute Difference	Adjusted Difference	95% Confidence Interval	P-value
1	654	0.25	0.125	0.116	(0.058, 0.172)	<0.001
2	1,306	0.50	0.118	0.109	(0.069, 0.151)	<0.001
3	1,958	0.75	0.106	0.099	(0.066, 0.135)	<0.001
4	2,612	1.00	0.029	0.029	(0.000, 0.059)	0.050

Table 5 - Interim Stopping Boundaries for 72-Hour Survival

The formal stopping boundaries are asymmetric, two-sided designs which are included in the unified family of group sequential stopping rules. (Table 5) The boundaries are asymmetric, because the utility/ease of use/training for a SGA is judged to be preferable to ETI. The tests for

superiority of either intervention will be based upon boundaries with parameters  $P=(0,0)$ ,  $R=(0.2,0.2)$ ,  $A=(0.355,0.29)$ , and  $\epsilon=c(1,1)$ , with a two-sided overall alpha level of 0.05.

We envision conducting 4 total analyses (3 interim + 1 final). The study does not include any futility boundaries because obtaining estimates in either direction will be informative; even an estimate that both treatments yield similar 72-hour survival is informative.

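### Section 15.5 lets any one of ten interaction tests, at no stated significance level and with no multiplicity allowance, trigger a stratified analysis, and does not say which analysis that is

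*Combined protocol and SAP*

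**What the plan says.** Section 15.5 opens: "We will explore multiplicative associations between airway management strategy (ETI vs. LT) and the pertinent subgroups, including". Nine bulleted factors follow, and a tenth, "Initial airway management with video laryngoscopy", runs into the closing paragraph. That paragraph ends with the operative rule: "If an [airway x subgroup] interaction is statistically significant, we will stratify the analysis by the subgroup".

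Five factors are fixed before the airway is managed:
- "Initial cardiac rhythm (shockable vs. non-shockable")
- "Bystander witnessed arrest (yes vs. no")
- "EMS response time (911 call to arrival on-scene", split at 10 minutes)
- whether the BLS unit can place an LT
- age, split at 65

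The other five are settled during care: time of airway placement, neuromuscular blockade, airway placed after ROSC, non-rebreather mask only, and video laryngoscopy.

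Three other places bear on the rule. Section 15.3 defines the primary analysis as the overall intention-to-treat difference with a robust standard error and 95% CI, and adds that "we will not stratify the primary analysis by initial cardiac rhythm". Section 16.2 commits to final primary-outcome estimates, intervals and p-values corrected for the stopping rule. Section 16.2 also lists, among the matters that may influence a stopping decision, "d) consistency of treatment effects across subgroups".

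**The concern.** Exploratory subgroup work normally describes the data. Here a significance test decides how the data are analysed and presented, and ten such tests each get a chance to do so. With no level and no adjustment stated, the probability that noise alone triggers a stratified analysis is neither fixed nor small.

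The rule also filters on significance. Strata are singled out when the interaction test happens to be significant, so the interactions a reader sees will tend to be exaggerated.

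The object of the rule is unclear as well. If the analysis to be stratified is the primary one, a significant rhythm interaction would call for what Section 15.3 excludes. If it is some other analysis, Section 15.5 does not name it. Nowhere does the plan say that the overall result remains the conclusion when an interaction is significant.

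At stake is a published statement that one airway strategy is better in one type of patient and the other strategy in another. It would rest on fractions of a sample that Section 16.1 sizes only for a 4.5-point overall difference.

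**Working it through.** The documents state no family-wise error for the interaction tests, so there is no planned figure to reproduce.

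**Inputs**
- Number of tests, k: 10 as listed in Section 15.5, or 5 if only the pre-treatment factors are kept. Section 12.2.2 permits video laryngoscopy for the intubation attempt, so that factor should be nearly empty in the LT arm and its interaction with assigned arm close to inestimable. Dropping it gives k = 9.
- Level per test, a: not stated. The 0.05 in Sections 16.1 and 16.2 is the overall level for the primary outcome. I assume 0.05 and show 0.01 and 0.10 beside it.
- No true effect modification, and one outcome.

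**Independent tests.** P(at least one significant) = 1 − (1 − a)^k.

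| a per test | k = 10 | k = 9 | k = 5 |
|---|---|---|---|
| 0.01 | 9.6% | 8.6% | 4.9% |
| 0.05 | 1 − 0.95^10 = 40.1% | 1 − 0.95^9 = 37.0% | 1 − 0.95^5 = 22.6% |
| 0.10 | 65.1% | 61.3% | 41.0% |

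**Correlated tests at a = 0.05.** The factors overlap, so the test statistics will be correlated to some degree. Simulating equicorrelated two-sided z-tests (400,000 draws) gives:

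| Pairwise correlation | k = 10 | k = 5 |
|---|---|---|
| 0 (check on the formula) | 40.0% | 22.6% |
| 0.1 | 39.5% | 22.5% |
| 0.2 | 37.6% | 21.8% |
| 0.3 | 35.2% | 21.0% |
| 0.5 | 28.7% | 18.3% |

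**Bound under any dependence.** k × a = 10 × 0.05 = 50%, or 5 × 0.05 = 25%. The 40% is therefore the independence value, not a maximum.

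**With adjustment.** Holm's first step is 0.05/10 = 0.005 for ten tests, 0.05/9 = 0.0056 for nine and 0.05/5 = 0.01 for five. With every null true, the chance of any rejection for ten independent tests is 1 − 0.995^10 = 4.9%.

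These figures count one test per factor on one outcome. Section 15.5 names no outcome, its list is worded as open-ended, and Sections 15.2 and 15.3 also plan as-treated analyses. Any of these could add tests.

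**The case against.** The strongest reply is that the trigger sentence sits in the subgroup section and governs only subgroup reporting. On that reading, stratum-specific estimates follow when an interaction test supports them, and requiring a significant interaction first is a recognised guard against over-reading subgroups. The section calls its work exploratory and claims no error control.

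Much of this stands. A reader might infer that a chance interaction would replace the overall result with stratum-specific conclusions, or that Section 15.5 reverses Section 15.3. The documents support neither. Section 15.3 fixes the overall comparison as primary, Section 16.2 commits to reporting it and applies its final boundary to it, and nothing in Section 15.5 withdraws either. The explicit exclusion of rhythm stratification also favours the narrower reading.

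It is fair, too, that 0.05 per interaction test is not in the plan, that ten overstates the number of estimable tests, and that the stopping link is loose. Section 16.2 lists subgroup consistency as something that may be weighed, apart from the formal boundaries, and nothing applies the Section 15.5 rule at interim looks.

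What does not stand is that exploratory wording makes the rule harmless. A gate protects against over-reading only if its error rate is known. Ten gates at an unstated level give no such assurance, and they select what is shown by significance. Holm adjustment of exploratory tests is a matter of judgement. Stating the level, the object of the rule and the standing of the overall result is not.

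**Conclusion.** The point holds as a gap in the subgroup rule. Taking 0.05 per test and no true effect modification, the chance that at least one false-positive interaction triggers stratified results is about 40% for ten independent tests, 37% for nine, and 29% for ten at correlation 0.5. For the five pre-treatment factors it is 23%, or 18% at correlation 0.5, so confining the list to those factors reduces the problem without removing it. The size depends heavily on the unstated level, which is itself a reason to state it.

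The consequence is a risk of spurious and selectively displayed subgroup claims. The primary test and its error control are not affected, and the overall estimate is not lost. Sections 15.3 and 15.5 do not flatly contradict each other, but they need reconciling because Section 15.5 leaves open which analysis it means.

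**What to change.** Replace the trigger sentence in Section 15.5 with wording such as:

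> The unstratified intention-to-treat difference remains the trial's conclusion whatever the interaction results. Subgroup estimates with 95% CIs and interaction p-values will be shown for all listed factors regardless of significance and labelled exploratory. Any claim of effect modification will be judged against a multiplicity-adjusted level (for example, Holm across the estimable factors at an overall 0.05).

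The plan should also say which factors count as estimable, given video laryngoscopy, and which outcome the interaction tests use.

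This changes wording only: no new data, no change to sample size or conduct. The cost is a somewhat lower chance of declaring a real interaction. The documents give no power for interactions, and every subgroup estimate would still be visible.

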## **16. Sample Size**

### **16.1 Sample Size Estimate**

The sample size estimate is based upon the primary outcome of 72-hour survival. Table 4 provides total sample size requirements to detect effect differences

	Statistical Power (1-β)		
Effect Size (Absolute Difference)	80%	85%	90%
4.0%	2,856	3,266	3,892
4.5%	2,284	2,612	3,112
5.0%	1,872	2,142	2,550

**Table 4 - Sample Size Estimates**  
Effect sizes based upon 13.7% baseline 72-hour survival.

in 72-hour survival after OHCA, with an overall significance level (adjusted for interim analyses) of 0.05 and accommodating up to a 5% loss of precision due to cluster randomization (with crossover).

The estimated effect sizes are based upon observations from the ROC PRIMED Trial. In ROC PRIMED, baseline 72-hour survival was 13.7%. There was a 5.0% absolute difference in 72-hour survival between ETI (13.7%) and SGA (8.7%). To account for potential confounders, for this trial we will use a more conservative figure of 4.5% to represent a minimal clinically significant difference. We designed the trial to have 85% power to detect this difference. Therefore, the required minimum sample size is 2,612 subjects (1,306 per group). To allow for subject withdrawal and loss to follow-up, we have budgeted to enroll up to a total of 3,000 subjects.

The participating US ROC sites (Alabama, Dallas, Milwaukee, Pittsburgh, Portland and San Diego) historically treated over 3,000 OHCA requiring advanced airway management in 2013. Therefore, we expect to have adequate capacity to enroll the requisite number of subjects over the anticipated three-year study period.

## 16.2 Interim Monitoring Plan and Stopping Boundaries – Criteria for Terminating the Trial

With input from the Data Safety and Monitoring Board (DSMB), prior to initiation of the trial, we will develop a monitoring plan to guide early termination of the trial. Factors influencing stopping decision may include (a) formal stopping rules based upon the primary analysis, (b) information on safety outcomes by treatment group, (c) consistency between results for primary and secondary outcomes, and (d) consistency of treatment effects across subgroups.

			Lower Stopping Boundary (SGA Better)			
Analysis	Cum. Sample Size	Prop. Max Stat Info	Absolute Difference	Adjusted Difference	95% Confidence Interval	P-value
1	654	0.25	-0.108	-0.098	(-0.154, -0.041)	0.001
2	1,306	0.50	-0.102	-0.092	(-0.135, -0.053)	<0.001
3	1,958	0.75	-0.092	-0.084	(-0.120, -0.052)	<0.001
4	2,612	1.00	-0.029	-0.029	(-0.059, 0.000)	0.050

			Upper Stopping Boundary (ETI Better)			
Analysis	Cum. Sample Size	Prop. Max Stat Info	Absolute Difference	Adjusted Difference	95% Confidence Interval	P-value
1	654	0.25	0.125	0.116	(0.058, 0.172)	<0.001
2	1,306	0.50	0.118	0.109	(0.069, 0.151)	<0.001
3	1,958	0.75	0.106	0.099	(0.066, 0.135)	<0.001
4	2,612	1.00	0.029	0.029	(0.000, 0.059)	0.050

Table 5 - Interim Stopping Boundaries for 72-Hour Survival

The formal stopping boundaries are asymmetric, two-sided designs which are included in the unified family of group sequential stopping rules. (Table 5) The boundaries are asymmetric, because the utility/ease of use/training for a SGA is judged to be preferable to ETI. The tests for

superiority of either intervention will be based upon boundaries with parameters  $P=(0,0)$ ,  $R=(0.2,0.2)$ ,  $A=(0.355,0.29)$ , and  $\epsilon=c(1,1)$ , with a two-sided overall alpha level of 0.05.

We envision conducting 4 total analyses (3 interim + 1 final). The study does not include any futility boundaries because obtaining estimates in either direction will be informative; even an estimate that both treatments yield similar 72-hour survival is informative.

At the conclusion of the clinical trial, reported point estimates, 95% confidence intervals, and p-values for the primary outcome will be adjusted for the true sampling distribution accounting for the stopping rule. Point estimates from interim analyses will be based on the bias adjusted point estimate. Confidence intervals and p-values will be calculated from the ordering of the outcome space based upon the maximum likelihood estimate. The stopping rules described above can be implemented using S+SeqTrial (S+SEQTRIAL User's Manual, Insightful, Inc., Seattle WA, 2000).

## **17. Eligibility for Participating and Remaining in the Enrollment Phase of the Trial**

Prior to entering the enrollment phase of the trial, each EMS agency must demonstrate readiness to participate in the study. EMS agencies must also meet select compliance benchmarks to remain the enrollment phase of the trial. Specific criteria for participating and remaining in the enrollment phase are listed in Appendix 3.

The trial will not have a formal run-in phase.

The study leadership will appoint a Study Monitoring Committee (SMC - Section 22) to oversee and review EMS agency study compliance. The SMC will meet on a bi-monthly basis to review enrollment and protocol adherence. The SMC will have the authority to recommend removal of an EMS agency from trial participation for protocol or data collection noncompliance.

## **18. Timeline**

### **18.1 Milestones for the Planning Phase**

The Year 1 planning phase of this trial is scheduled for September 15, 2014 - July 30, 2015. The parameters of the grant award for this trial specify that the certain milestones must be met during the Year 1 planning phase prior to proceeding to the Year 2-5 trial execution/subject enrollment phase.

Tasks that will be completed during the Year 1 planning phase include:

- Develop and finalize trial protocol;
- Register trial at [www.clinicaltrials.gov](http://www.clinicaltrials.gov);
- Obtain Food and Drug Administration (FDA) review for Investigational Device Exemption (IDE);
- Finalize selection and definition of data elements;
- Program and test data base;

- Obtain initial Institutional Review Board (IRB) approval;
- Initiate Exception from Informed Consent (EFIC) community consultation and public disclosure (CC/PD);
- Develop and test EMS training materials;
- Establish site subawards.

A program evaluation will be performed by an independent agency appointed by NHLBI.

## **18.2 Milestones for Trial Execution and Subject Recruitment**

Trial execution and subject recruitment will occur over the 4-year period August 1, 2015 – July 30, 2019.

We expect 6 ROC regional coordinating centers encompassing over 33 EMS agencies to participate in the trial. We expect participating EMS agencies to complete a brief period (2-4 months) of data collection to demonstrate readiness for the enrollment phase of the trial. We expect recruitment of subjects to occur through July 30, 2018 (3 years). Trial close-out and analysis will occur during August 1, 2018 – July 30, 2019.

## **19. Data Sources and Management**

### **19.1 Data Sources**

Data will be collected prospectively as patient care progresses. This will include a review of all EMS and hospital records.

#### **19.1.1 Out-of-Hospital EMS Data**

Out-of-hospital data will be determined from EMS clinical care documentation, including EMS dispatch records and patient care records.

CPR process files will be collected and archived but will not be analyzed as part of the primary trial effort (although additional grant funding may support this effort in the future).

#### **19.1.2 Hospital Data**

Hospital records that will be reviewed for this trial may include:

- Emergency Department and inpatient physician clinical documentation
- Emergency Department and inpatient nurse clinical documentation
- Radiology reports
- Operative reports
- Procedural notes
- Discharge summary
- Death note and certificate

### 19.1.3 Post-Discharge Vital Status

This trial will not require the determination of post-discharge vital status.

## 19.2 Data Entry

The DCC will provide web-based HTML forms to collect necessary information from the participating sites. Web entry forms will have dynamic features such as immediate checks on data and relationships within a form and between forms. Details and clarification about data items will be provided using pop-up windows and links to appropriate sections of the on-line version of the Manual of Operations. Data encryption and authentication methods will be used. The DCC will build additional features into the web entry forms including: forms transmission history, access to past forms, tracking of data corrections, and the capability to save and re-load incomplete forms.

## 19.3 Database Management

The DCC will use a two-tiered database structure. A front-end database will serve the web entry needs, using a database management system well-suited to handling updates from multiple interactive users. The data from this database will be transferred periodically (e.g., weekly) to a data repository that can be used by statistical software packages. These data sets will be the basis for data queries, analyses and monitoring reports. Various versions of this database will be kept as needed, e.g., for quarterly performance reports. Backup of data and programs will be performed at frequent intervals. Access to data will be limited to those who need access to perform their tasks. The database management system is able to manage large quantities of data, to merge data from multiple databases as required, to handle complex and possibly changing relationships, and to produce analysis datasets that can be imported into a variety of statistical analysis packages.

## 20. EMS Research Protocol Training

### 20.1 Overview of EMS Protocol Training Elements

Training of EMS personnel for this trial will encompass didactic and practical modalities. The salient components of EMS personnel training are described below. While we will develop a master set of training materials, individual regional coordinating centers will be permitted to customize the format to suit local needs.

Prior to entering the trial, participating EMS agencies will summarize their experience with and standard training practices (format, frequency) for both airway devices.

All participating EMS agencies will receive initial training in the trial protocol. Key elements of training will include:

- **Scientific Basis for the Trial** – This section include level-appropriate presentation of the scientific principles of airway management, a summary of prior studies of OHCA airway management, and the rationale for the current randomized trial. All EMS personnel that may potentially carry out study procedures will be required to undergo training.
- **Review of Study Protocol** – This section will include the following: overall study design, inclusion and exclusion criteria, the process of exception to informed consent under

emergency circumstances, the study protocol and procedures, data reporting, and contingency measures.

- **Protocol Practicum** – EMS personnel will have the opportunity to simulate execution of the trial protocol in “hands-on” fashion. This practical experience will encompass the use of mannequins that can accommodate ETI and LT insertion. EMS personnel will be given the opportunity to practice to proficiency each component of the protocol. EMS personnel will have the opportunity to integrate the trial procedures in the context of other ACLS interventions. Various permutations of the study protocol will be presented, including each of the study arms and scenarios with unsuccessful initial airway attempts.
- **Data Reporting** – Select data elements specific to airway management are required for this trial; for example, the sequence of airway interventions, the number of attempts, the timing of successful airway insertion, and adverse events. The training will review definitions and reporting practices for each of these data elements.
- **Cognitive Post-Test** – A cognitive post-test will cover key trial procedures and may be completed online or as a written or verbal component of the training sessions. A record of training completion will be maintained by each site or EMS agency.

